24. Clinically significant deviation from normal in physical examination, vital signs, or clinically laboratory tests at Screening or Baseline
25. A prolonged QT/ corrected QT interval (QTc) interval (QTc >450 msec) at Screening or Baseline as demonstrated by average QTc interval from triplicate ECGs. A history of risk factors for torsade de pointes (eg, heart failure, hypokalemia, family history of long QT Syndrome) or the use of concomitant medications that prolong the QT/QTc interval.
26. Any other abnormality of the ECG at Screening or Baseline (including QRS >110 msec, abnormal electrical axis, PR interval >220 msec and conduction abnormalities) considered clinically significant by the investigator
27. Left bundle branch block at Screening or Baseline
28. Persistent heart rate <50 or >100 beats per minute (bpm) at Screening or Baseline

29. Persistent systolic blood pressure (BP) >165 mmHg or <90 mmHg and diastolic BP >100 mmHg or <60 mmHg at Screening
30. History of cardiac arrhythmias. Subjects with other heart diseases (eg, ischemic heart disease, clinically significant valvular heart disease) that are not stably and adequately controlled, or uncompensated heart failure (New York Heart Association Class III and Class IV)
31. Type 1 or Type 2 diabetes mellitus that is not well controlled
32. Malignant neoplasms within 5 years before Screening (except for basal or squamous cell carcinoma in situ of the skin, or localized prostate cancer that did not require systemic therapy; these do not exclude the subject). Subjects who had malignant neoplasms but who have had at least 5 years of documented evidence of no active disease before Screening need not be excluded.
33. Medical conditions (eg, cardiac, respiratory, gastrointestinal, renal disease) that are not stably controlled, or which, in the opinion of the investigator(s), could affect the subject's safety or interfere with the study assessments
34. Hypopigmentation conditions (eg, albinism and vitiligo)
35. Known or suspected history of drug or alcohol dependency or abuse within 2 years before Screening, current use of recreational drugs or a positive urine drug test at Screening. Subjects who test positive in the urine drug screen need not be excluded if in the clinical opinion of the investigator, this is due to the subject taking prior/concomitant medications for a medical condition that is not exclusionary and not due to drug abuse.

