9.4.7 Prior and Concomitant Therapy

Medication (including over-the-counter medications) or therapy administered to the subject before the study (within 6 months of randomization) and during the study (starting at the date of informed consent) will be recorded on the Prior & Concomitant Medication eCRF or Non-Pharmacological Procedures eCRF. The investigator will record on the Adverse Event eCRF any AE for which the concomitant medication/therapy was administered. If the concomitant medication/therapy is being administered for a medical condition present at the time of entry into the study, the investigator will record the medical condition on the Medical History and Current Medical Condition eCRF.

Listings of prohibited and permitted drugs are provided in [Appendix 2](#). Prohibited medications are presented in [Listing 1](#), [Listing 2](#), [Listing 3](#), [Listing 4](#), [Listing 5](#), and [Listing 6](#). Medications that are permitted with restrictions are listed in [Listing 7](#), [Listing 8](#), and [Listing 9](#).

The following agents are not permitted before randomization (specific timeframes are shown below) and throughout the study until after the last treatment visit:

- Anticoagulants (eg, warfarin, digabatin) are not permitted for a period of 5 half-lives or 7 days (whichever is longer) before randomization
- Drugs which may cause QTc prolongation are not permitted for a period of 5 half-lives or 14 days (whichever is longer) before randomization
- Strong CYP3A4 inhibitors are not permitted for a period of 5 half-lives or 14 days (whichever is longer) before randomization
- Live vaccines are not permitted within 3 months before randomization. This does not apply to non-live/inactivated vaccines
- Ig therapy and biologic drugs are not permitted within 6 months before randomization
- Systemic or ocular immunosuppressive or immunomodulatory drugs are not permitted for a period of 5 half-lives or 60 days (whichever is longer) before randomization

Subjects taking AChEIs or memantine must meet the following criteria in order to be included in the primary analyses:

- On a stable dose for 12 weeks before the Baseline cognitive assessments at Visit 2
- Remain on a stable dose while on study

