Subjects who initiate treatment with an AChEI or memantine during the study, or who change their dose of AChEI or memantine while on study, will be allowed to continue in the study, but their clinical efficacy data will be censored from the time of drug initiation for the primary analyses.

Subjects taking all other non-prohibited concomitant medications must meet the following requirements:

- Must be on stable dose for at least 4 weeks before randomization, except for medications that are administered as short courses of treatment or which are to be used intermittently as needed
- Medications that are used as needed, rather than on a stable daily basis, and which are central nervous system (CNS) active and may affect cognitive function, are not permitted during a period of 72 hours before cognitive testing

Subjects who initiate treatment with or have dose adjustment of drugs not intended for treatment of cognitive impairment during the study may continue in the study if in the opinion of the investigator this will not interfere with study procedures or subject safety, and are not prohibited above. If the subject initiates treatment for co-morbidities with a (non-prohibited) drug that may affect cognitive function, the subject should not have cognitive assessments performed until the dose has been stable for at least 4 weeks.

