Appendix 2 **List of Permitted and Prohibited Prior/Concomitant Medications**

Prohibited medications are shown in [Listing 1](#), [Listing 2](#), [Listing 3](#), [Listing 4](#), [Listing 5](#), and [Listing 6](#). Medications permitted with restrictions are listed in [Listing 7](#), [Listing 8](#), and [Listing 9](#). **These may not be all-inclusive listings.** Please contact the medical monitor(s) if the investigators have any questions or concerns regarding any medication not listed that your subjects may be taking before enrollment or start during the course of the E2609-G000-202 study.

Antibiotics, analgesics, and anti-inflammatory drugs intended for short courses of treatment are permitted and do not need to follow the restrictions of [Listing 9](#) for a stable dose of 4 weeks before Baseline. If these medications may affect cognitive function but the medications are clinically indicated, then cognitive testing should not take place until at least 72 hours after the last dose of the course of treatment.

Prohibited Prior/Concomitant Medications**Listing 1 Drugs with High Risk of Torsades de Pointes or QTc Prolongation**

| Generic name | Brand name (Names shown are not exhaustive and are examples only; names may be the ® or ™) | Comments |
|---|--|---|
| Prohibited from 14 days (or 5 half-lives, whichever is longer) before Randomization until after the last treatment visit | | |
| Anti-arrhythmic/ abnormal heart rhythm | | |
| Amiodarone | Cordarone; Pacerone | Incidence in females greater than males, Torsades de Pointes risk regarded as low |
| Disopyramide | Norpace | Incidence in females greater than males |
| Dofetilide | Tikosyn | |
| Ibutilide | Corvert | Incidence in females greater than males |
| Procainamide | Pronestyl; Procan | |
| Quinidine | Cardioquin; Quinaglute | Incidence in females greater than males |
| Sotalol | Betapace | Incidence in females greater than males |
| Antihistamine/ allergic rhinitis | | |
| Astemizole | Hismanal | No longer available in United States |
| Terfenadine | Seldane | No longer available in United States |
| Anti-anginal/ heart pain | | |
| Bepridil | Vascor | Incidence in females greater than males |
| Antibiotic/ bacterial infection | | |
| Clarithromycin | Blaxin | |
| Moxifloxacin | Avelox | |
| Sparfloxacin | Zagam | |
| Listing 1 continued | | |
| Antimalarial/ malaria infection | | |
| Chloroquine | Aralen | |
| Halofantrine | Halfan | Incidence in females greater than males |

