| Antipsychotic/ anti-emetic/ schizophrenia/ nausea | | |
| Chlorpromazine | Thorazine | |
| Gastrointestinal stimulant/ heartburn | | |
| Cisapride | Propulsid | |

Listing 1 Drugs with High Risk of Torsades de Pointes or QTc Prolongation

| Generic name | Brand name (Names shown are not exhaustive and are examples only; names may be the ® or ™) | Comments |
|--|--|---|
| Antinausea/ nausea | | |
| Domperidone | Motillum | Not available in the United States |
| Sedative; antinausea/ anesthesia adjunct, nausea | | |
| Droperidol | Inapsine | |
| Antibiotic; gastrointestinal stimulant/ bacterial infection; increase gastrointestinal motility | | |
| Erythromycin | Erythrocin; E.E.S. | Incidence in females greater than males |
| Antipsychotic/ schizophrenia | | |
| Haloperidol | Haldol | When given intravenously or at higher than recommended doses, risk of sudden death, QT prolongation, and torsades increases |
| Mesoridazine | Serentil | |
| Thioridazine | Mellaril | |
| Opiate agonist/ pain control, narcotic dependence | | |
| Levomethadyl | Orlaam | |
| Methadone | Methadose; Dolophine | Incidence in females greater than males |
| Anti-infective/ pneumocystis pneumonia | | |
| Pentamidine | Pentam; NebuPent | Incidence in females greater than males |
| Antipsychotic/ Tourette's tics | | |
| Pimozide | Orap | Incidence in females greater than males |
| Antilipemic/ hypercholesterolemia | | |
| Probucol | Lorelco | No longer available in United States |
| Anticancer | | |
| Arsenic trioxide | Trisenox | Used for leukemia |
| Vandetanib | Zactima | Used for thyroid cancer |

Note: This list is not exhaustive.

QTc = Corrected QT interval.

Listing 2 Prohibited Medications Within 7 Days (or 5 Half-lives, Whichever is Longer) Before Randomization and Until after the Last Treatment Visit)

| Generic Name | Brand name (Names shown are not exhaustive and are examples only; names may be the ® or ™) |
|---|--|
| Anticoagulants | |
| Adeporin | Normiflo |
| Alteplase, tPA | Activase, Cathflo Activase |
| Anisindione | Miradon |
| Antithrombin III | ATryn, Thrombate III |
| Argatroban | Argatroban |
| Bivalirudin | Angiomax |
| Dabigatran | Pradaxa |
| Dalteparin | Fragmin |
| Danaparoid | Orgaran |
| Dicumarol | Dicumarol |
| Enoxaparin | Lovenox |
| Fondaparinux | Arixtra |
| Heparin Sodium | Monoject |
| Lanoteplase | Lanoplas |
| Lepirudin | Refludan |
| Pentosan polysulfate sodium | Elmiron |
| Reteplase | Retavase, Retevase |

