| Amitriptyline | (various) |
| Chlordiazepoxide | H-Tran, Librium |
| Clonazepam | Ceberclon, Klonopin |
| Diazepam | Diastat, Dizac, Valium |
| Dothiepin | (various) |
| Estazolam | ProSom |
| Flunitrazepam | Rohypnol |
| Flurazepam | Dalmane |
| Lorazepam | Ativan |
| Midazolam | Versed |
| Olanzapine | Zyprexa |
| Promethazine | Phenergan; others |
| Ramelteon | Rozerem |
| Risperidone | Risperdal |
| Temazepam | Restoril |
| Triazolam | Halcion |
| Zolpidem | Ambien; others |
| Zopiclone | (various) |
| Other benzodiazepines, tricyclic antidepressants, antipsychotics and other drugs which are used on PRN basis as sedatives | |

Note: This list is not exhaustive

PRN = Pro re nata

Listing 9 Permitted Centrally Active or Psychiatric Medications

| Generic Name | Brand name (Names shown are not exhaustive and are examples only; names may be the ® or ™) |
|--|--|
| If to be used on a PRN basis see Listing 8 . If to be used chronically, subjects must be on a stable dose for ≥4 weeks before Baseline. Changes in dose or initiation of new concomitant medications for chronic use (not PRN use) is permitted but if the medication affects cognitive function, do not conduct cognitive testing until the dose is stable for 4 weeks. | |
| Antidepressants | |
| Amitriptyline hydrochloride | Elavil |
| Amoxapine | Amoxapine |
| Bupropion | Aplenzin, Budeprion, Buproban, Zyban, Wellbutrin |
| Citalopram | Celexa |
| Clomipramine hydrochloride | Anafranil |
| Desipramine hydrochloride | Norpramin |
| Desvenlafaxine | Pristiq |
| Doxepin hydrochloride | Prudoxin, Silenor, Sinequan, Zonalon |
| Duloxetine | Cymbalta |
| Escitalopram | Lexapro |
| Fluoxetine | Prozac, Sarafem, Selfemra |
| Fluvoxamine | Luvox |
| Imipramine hydrochloride | Tofranil |
| Isocarboxazid | Marplan |
| Maprotiline hydrochloride | Ludiomil |
| Mirtazapine | Remeron Soltab |
| Nortriptyline hydrochloride | Aventyl, Pamelor |
| Paroxetine | Paxil, Pexeva |
| Phenelzine | Nardil |
| Protriptyline hydrochloride | Vivactil |
| Rasagiline | Azilect |
| Selegiline | EMSAM |
| Sertraline | Sertaraline, Zoloft |
| Tranlycypromine | Parnate |
| Trazodone hydrochloride | Desyrel, Oleptro |
| Trimipramine maleate | Surmontil |
| Venlafaxine hydrochloride | Effexor |

Listing 9 Permitted Centrally Active or Psychiatric Medications

| Generic Name | Brand name (Names shown are not exhaustive and are examples only; names may be the ® or ™) |
|---|--|
| Mood Stabilizers (Listing 8 continued) | |

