| Carbamazepine | Carbatrol, Epitol, Equetro, Tegretol, Tegretol XR |
| Lamotrigine | Lamictal, Lamictal CD, Lamictal ODT, Lamictal XR |
| Valproic acid | Depacon, Depakene, Depakote, Depakote ER, Divalproex Sodium, Stavzor, Valproate |
| Antipsychotics | |
| Acetophenazine | Tindal |
| Aripiprazole | Abilify |
| Asenapine | Saphris |
| Olanzapine | Zyprexa |
| Chlorpromazine | Thorazine |
| Haloperidol | Haloperidol, Haldol |
| Clozapine | Clozaril, Fazacllo |
| Fluphenazine | Prolixin |
| L-Methylfolate | Deplin, L-Methylfolate Calcium |
| Loxapine | Loxitane |
| Mesoridazine | Serentil |
| Perphenazine | Trilafon |
| Quetiapine | Seroquel |
| Risperidone | Risperdal |
| Thioridazine | Mellaril |
| Thiothixene | Navane |
| Trifluoperazine | Stelazine |
| Benzodiazepines | |
| Alprazolam | Alprazolam Intensol, Niravam, Xanax |
| Chlordiazepoxide | H-Tran, Librium |
| Clonazepam | Ceberclon, Klonopin |
| Diazepam | Diastat, Dizac, Valium |
| Estazolam | ProSom |
| Flunitrazepam | Rohypnol |
| Flurazepam | Dalmane |

Listing 9 Permitted Centrally Active or Psychiatric Medications

| Generic Name | Brand name (Names shown are not exhaustive and are examples only; names may be the ® or ™) |
|--------------|--|
| Lorazepam | Ativan |
| Midazolam | Versed |
| Temazepam | Restoril |
| Triazolam | Halcion |
| Zopiclone | Imovane, Zimovane |
| Zopidem | Ambien, Ambien CR, Intermezzo, Stilnox, Stilnoct, Sublinox, Hypnogen, Zolsana |

Note: This list is not exhaustive.

PRN = Pro re nata

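### Listing 9 permits four antipsychotics that Listing 1, Section 9.4.7 and exclusion criterion 25 bar as QT-prolonging drugs

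*Protocol*

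**What the plan says.** Listing 1 in Appendix 2 covers drugs with a high risk of torsades de pointes or QTc prolongation. Its rule is "Prohibited from 14 days (or 5 half-lives, whichever is longer) before Randomization until after the last treatment visit". Among the drugs it names are chlorpromazine, haloperidol, mesoridazine and thioridazine.

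Listing 9 covers permitted centrally active or psychiatric drugs. It allows chronic use on a dose stable for at least 4 weeks before Baseline and states that "Changes in dose or initiation of new concomitant medications for chronic use (not PRN use) is permitted"; the only restriction on such a change is on when cognitive testing may take place. Its antipsychotic rows include "Chlorpromazine | Thorazine" and "Haloperidol | Haloperidol, Haldol", together with mesoridazine and thioridazine. For as-needed use it refers to Listing 8, which ends with a general row: "Other benzodiazepines, tricyclic antidepressants, antipsychotics and other drugs which are used on PRN basis as sedatives".

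In the body text, Section 9.4.7 states "Drugs which may cause QTc prolongation are not permitted for a period of 5 half-lives or 14 days (whichever is longer) before randomization", under a lead-in that extends the ban through the treatment period. Exclusion criterion 25 (Section 9.3.2) rules out "the use of concomitant medications that prolong the QT/QTc interval", and criterion 37 rules out breaches of the medication restrictions.

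**The concern.** The same four drugs are banned by name in one listing and allowed by name in another, and nothing in Appendix 2 says which listing prevails. Two decisions at the site are affected. At entry, a subject on stable haloperidol meets Listing 9 but fails Section 9.4.7 and criterion 25. During treatment, Listing 9 lets an investigator start or adjust one of these drugs when the protocol means to forbid it.

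A site that reads the whole protocol will find the ban. A site that looks the drug up in Listing 9 will find it expressly allowed. The appendix's prompt to contact the medical monitor concerns drugs that are not listed, so it does not reach these four. At stake are subject safety and correct eligibility. QT prolongation caused by such a drug could also trigger discontinuation of study drug under Section 9.3.3 (g, h) and blur the QTcF summaries planned in Section 9.7.1.8.5.

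**Working it through.** No sample size, power or alpha is involved. The check is a comparison of the lists and of the ECG schedule.

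**1. Cross-match of the listings**

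| Drug | Listing 1 (prohibited) | Listing 9 (permitted) |
|---|---|---|
| Chlorpromazine | yes | yes |
| Haloperidol | yes | yes |
| Mesoridazine | yes | yes |
| Thioridazine | yes | yes |
| Pimozide | yes | no |

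Listing 1 has 30 drugs and Listing 9 has 17 under antipsychotics; 4 are in both. These are 4 of the 5 drugs that Listing 1 labels antipsychotic. The haloperidol comment in Listing 1 says that risk rises with intravenous use or high doses. It describes risk and exempts nothing.

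**2. As-needed use**

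None of the drugs named in Listing 8 is in Listing 1 (0 matches), so this route runs only through the general rows. The sedative row is wide enough to take in droperidol, which Listing 1 labels a sedative. The opioid row is wide enough to take in methadone and levomethadyl, which Listing 1 also bans.

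**3. Which text is the error**

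Section 9.4.7 bars QTc-prolonging drugs throughout treatment. Its stable-dose and as-needed conditions are introduced by "Subjects taking all other non-prohibited concomitant medications must meet the following requirements", and it confines on-study starts and dose changes to drugs it has not already prohibited. Criterion 25 points the same way at entry. Everything outside Listing 9 therefore supports the ban. Nefazodone shows the intended treatment: it is banned in Listing 6 and absent from Listing 9.

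**4. ECG gaps**

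Table 7 schedules on-treatment ECGs at Visits 5, 7, 9, 11, 14, 16 and 18, which are Weeks 2, 4, 8, 12, 26, 52 and 78 after first dose.

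- 4 − 2 = 2 weeks
- 8 − 4 = 4 weeks
- 12 − 8 = 4 weeks
- 26 − 12 = 14 weeks
- 52 − 26 = 26 weeks
- 78 − 52 = 26 weeks

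The QTcF stopping rules act only when an ECG is taken. After Week 26, a drug begun just after one ECG could run about 26 weeks before the next scheduled one.

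**5. Size of the study drug's own signal**

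Section 7.1 reports a QTcF rise of 14.9 msec after a single 800 mg dose. The highest dose here is 50 mg daily. The nominal ratio is 800 / 50 = 16, but it sets a single dose against daily dosing and is not an exposure ratio.

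**The case against.** The strongest reply is that precedence is already settled. Section 9.4.7 introduces the listings, bans the class, and limits every allowance to drugs it does not prohibit. On that reading, what is left is four stray rows. This is right about the intended rule, but it does not make Listing 9 harmless, because the listing does not repeat the limit and names the drugs as permitted.

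The as-needed point is weaker than the Listing 9 point. The general row in Listing 8 names no banned drug, and the as-needed condition in Section 9.4.7 sits under the non-prohibited heading. The case rests on Listing 9.

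The safeguards are real:

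- QTc above 450 msec is excluded at entry.
- QTcF criteria stop study drug.
- ECGs can be taken at unscheduled visits.
- Exclusion criterion 6 removes many subjects likely to need an antipsychotic at entry.
- An on-study start requires the investigator to judge that safety is not compromised.
- Concomitant medication is reviewed at every visit from Visit 4, including Weeks 39 and 65, so a new drug would be seen within about 13 weeks (39 − 26) after Week 26. A reviewer who consults Listing 9 would, however, find the drug allowed.

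It is also true that only Listing 1 names the four drugs, since Section 9.4.7 and criterion 25 work by class, and that criterion 25 governs entry only. Neither point removes the conflict.

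**Conclusion.** The contradiction stands. Four named drugs are both prohibited and permitted in the current Appendix 2, and the rest of the protocol shows that the prohibition is the intended rule. It should be corrected, because Listing 9 is operational text that can lead a site to enrol or treat a subject against the protocol.

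The consequence is limited by the entry QTc limit and the QTcF stopping rules. The 26-week figure is an upper bound on the time to the next scheduled ECG. It assumes that the drug is started just after an ECG from Week 26 onward and that no unscheduled ECG is taken. How many subjects would be exposed cannot be derived from the protocol, and no planned statistical figure changes.

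**What to change.** Delete chlorpromazine, haloperidol, mesoridazine and thioridazine from Listing 9. Add one sentence to Appendix 2: *Listings 1 to 6 prevail over Listings 7 to 9; a drug in Listings 1 to 6 is not permitted by any later listing, including the catch-all rows.* The sentence is needed because deleting rows from Listing 9 leaves the general rows of Listing 8 as they are. It would be sensible to extend it to the opening paragraph of Appendix 2 on short courses of antibiotics and analgesics, since Listing 1 bans several antibiotics and methadone.

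The cost is four rows and one sentence, issued as an amendment with notice to sites. Under Section 11.1, regulatory submission and further IRB/IEC approval are needed if the change is classed as specifically affecting subject safety. No design element or analysis changes.

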Appendix 3 Pharmacodynamic, Pharmacogenomic, and Other Biomarker Research

Subjects enrolled in this clinical study will have biologic samples collected for PD, PGx, and other biomarker analysis. These samples may be used for discovery and validation to identify biomarkers that may be used for exploratory evaluation of response or safety-related outcomes as well as for use in diagnostic development.

The PGx samples may be used to identify genetic factors that may influence a subject's exposure to the study drug, as well as genetic factors that may have an effect on clinical response or potential AEs related to study drug, and to explore the role of genetic variability in response. Samples may be analyzed to determine a subject's genotypes or sequence for a number of genes or non-coding regulatory regions. The research may include the investigation of polymorphisms in genes that are likely to influence the study drug PK or therapeutic response.

Collection of the PD, PGx, and other biomarker samples will be bound by the sample principles and processes outlined in the main study protocol. Sample collection for PD, PGx, and other biomarker analysis is required as per the study protocol unless the collection and use of the samples is prohibited by specific country laws.

Sample Collection and Handling

The samples will be collected according to the study flow chart. If, for operational or medical reasons, the genomic DNA blood sample cannot be obtained at the prespecified visit, the sample can be taken at any study center visit at the discretion of the investigator and site staff.

Security of the Samples, Use of the Samples, Retention of the Samples

Sample processing, for example DNA or RNA extraction, genotyping, sequencing, or other analysis will be performed by a laboratory under the direction of the sponsor. Processing, analysis, and storage will be performed at a secure laboratory facility to protect the validity of the data and maintain subject privacy.

Samples will only be used for the purposes described in this protocol. Laboratories contracted to perform the analysis on behalf of the sponsor will not retain rights to the samples beyond those necessary to perform the specified analysis and will not transfer or sell those samples. The sponsor will not sell the samples to a third party.

Samples will be stored for up to 15 years after the completion of the study (defined as submission of the clinical study report to the appropriate regulatory agencies). At the end of the storage period, samples will be destroyed. Samples may be stored longer if a health authority (or medicinal product approval agency) has active questions about the study. In this special circumstance, the samples will be stored until the questions have been adequately addressed.

It is possible that future research and technological advances may identify genomic variants of interest, or allow alternative types of genomic analysis not foreseen at this time. Because it is not possible to prospectively define every avenue of future testing, all samples collected will be single or double coded (according to the ICH E15 guidelines) in order to maintain subject privacy.

Right to Withdraw

If, during the time the samples are stored, a participant would like to withdraw his/her consent for participation in this research, Eisai will destroy the samples. Information from any assays that have already been completed at the time of withdrawal of consent will continue to be used as necessary to protect the integrity of the research project.

Subject Privacy and Return of Data

No subject-identifying information (eg, initials, date of birth, government identifying number) will be associated with the sample. All PD and other biomarker samples will be single coded. Genomic DNA samples used to explore the effects on PK, treatment response, and safety will be single coded. Genomic DNA samples that will be stored for long-term use (defined as 15 years after the completion of the study) will be double coded. Double coding involves removing the initial code (subject ID) and replacing with another code such that the subject can be re-identified by use of 2 code keys. The code keys are usually held by different parties. The key linking the sample ID to the subject number will be maintained separately from the sample. At this point, the samples will be double-coded, the first code being the subject number. Laboratory personnel performing genetic analysis will not have access to the “key.” Clinical data collected as part of the clinical trial will be cleaned of subject identifying information and linked by use of the sample ID “key.”

The sponsor will take steps to ensure that data are protected accordingly and confidentiality is maintained as far as possible. Data from subjects enrolled in this study may be analyzed worldwide, regardless of location of collection.

The sponsor and its representatives and agents may share coded data with persons and organizations involved in the conduct or oversight of this research. These include:

- CROs retained by the sponsor
- IECs or IRBs that have responsibility for this research study
- National regulatory authorities or equivalent government agencies

At the end of the analysis, results may be presented in a final report which can include part or all of the coded data, in listing or summary format. Other publication (eg, in peer-reviewed scientific journals) or public presentation of the study results will only include summaries of the population in the study, and no identified individual results will be disclosed.

Given the research nature of the PD, PGx, and other biomarker analysis, it will not be possible to return individual data to subjects. The results that may be generated are not

currently anticipated to have clinical relevance to the patients or their family members. Therefore, these results will not be disclosed to the patients or their physicians.

If at any time, PD, PGx, or other biomarker results are obtained that may have clinical relevance, IRB review and approval will be sought to determine the most appropriate manner of disclosure and to determine whether or not validation in a Clinical Laboratory Improvement Amendments-certified setting will be required. Sharing of research data with individual patients should only occur when data have been validated by multiple studies and testing has been done in Clinical Laboratory Improvement Amendments-approved laboratories.

